**Neuroimaging.** MRI data will be acquired from participants **at UAB only** (n=50) at baseline and 4 months. Participants will undergo ~1 hour of scanning at each time point, using a 3T Siemens Prisma scanner with a 64 channel coil, housed at the UAB Civitan International Neuroimaging Laboratory (CINL), where Co-I [name] is the Co-Director. Participants will be screened for any contraindications for MRI (described below in risks). We will acquire anatomical (T1 and T2 scans), arterial spin labeling (pseudo-continuous ASL), and resting state blood oxygenation level dependent (BOLD) scans. ASL, a non-invasive approach to measuring cerebral blood flow (CBF), is a MRI technique that measures tissue perfusion (blood flow), by using magnetically-labeled arterial blood water protons as an endogenous tracer. ASL has demonstrated high consistency with positron emission tomography PET measurement of CBF, and is emerging in popularity due to its advantages in terms of cost-effectiveness and safety. General quality assurance procedures will be followed as data are acquired, including quality control checks after each session. Mean global CBF, and regional blood flow to the hippocampus will be measured for each participant based on ASL scans. We will also measure changes in total gray matter volume and hippocampal volume (mm^3) using Freesurfer. Strength of connectivity within the default mode network will also be

examined based on resting state BOLD data (i.e., average correlations of BOLD-signal time series of distributed brain regions as in previous work). BOLD data will be preprocessed according to strict quality control methods, including motion scrubbing, implemented by XCP engine with fMRI prep, and regression of confounds including but not limited to motion, heartbeat and respiration.

**Psychological mechanisms of adherence (MoA)** measures will be assessed at the new 12-month visit only. The trait-level measures (i.e., paper/pencil surveys completed in person) capture aggregate perceptions about one's self, whereas text message (i.e. ecological momentary assessment [EMA]) (state-level) items reflect experiences in the moment. The measures chosen are theory-driven, align with the NIH Science of Behavior Change. As noted in the Table below, abbreviated versions of select measures used in lab visits will be used in EMA to reduce participant burden and increase compliance.

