Following the 12 month visit, the EMA will include 7-days of twice daily texts (quasi-random times at morning and evening) using their own mobile device. **Participants will already be familiar with texting procedures following the behavioral coaching intervention (part of primary study, described above and below).** The Twilio 3rd party add on feature in RedCap will be used to generate links to our RedCap survey (assessing items indicated in the Table) housed within the Denver RedCap server and text message them to participant's cell phones. No data is sent to Twilio and no PHI is collected. Twilio is HIPPA compliant and is vetted by RedCAP admin/Denver CCTSI. We piloted the survey, which takes <five minutes. If a participant does not respond to a survey, a reminder message will be sent one hour later. If a participant has not responded to any survey for 24 hours, we will contact them to troubleshoot and encourage reporting. **Actigraphy will also be worn for 7 days, using procedures described above for the Primary Study.**

We will administer individual interviews with a subset of participants (~n=25) to determine factors that drive or impede long-term PA after having been in a supervised intervention.

| Mechanisms of Adherence Measures in the New 12 month Follow Up |   |
|--|---|
| Construct  | Measure   |
| Self-Efficacy  | Lab and EMA: 9-item self-efficacy exercise (SEE) scale  assesses expectations related to ability to continue to exercise in the face of barriers (How confident are you right now that you could exercise three times per week for 20 minutes if: [e.g., "You did not enjoy it", "You were too busy", "You had to exercise alone"]?). EMA in am and pm; items use words "today" and "tomorrow".   |

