For EMA data, a linear mixed regression model including random effects for subject and day (within-subject) to account for the multilevel structure of the data will be used to examine the time-lagged effects of MoA variables occurring during a specified time interval (T-1) on PA during the subsequent (lagged) time interval (T) within each day of monitoring:  $\text{PA}(T) = \text{MoA}(T-1) + \text{Time of Day} + \text{Day} + \text{site} + \text{covariates}$ . The time interval T can be time of day or different days, for example we can use the MoA in Day 1 to predict the PA in Day 2 or use the MoA in the morning to predict the PA later in the same day. The covariates include significant distal predictors. Moderating effects will be explored by including interaction terms in above model. Concurrent effects of these MoA variables on PA (i.e., both the predictor and outcome were assessed during the same time interval) will also be examined. To explore whether the MoA variables mediate intervention (HIIT vs CME and coaching texting vs control) effects on PA, mediation analyses with focus on effect estimation rather than hypothesis testing will be conducted using path analysis with methods considering the multi-level nature of data and robust to non-normality (e.g., cluster bootstrapping), assuming a causal chain of the form: Intervention (HIIT vs CME) --> effect on MoA [as mediator] --> effect on PA. Using the estimated path coefficients, direct, indirect, and total effects will be estimated and uncertainty on these estimates be estimated computed in the form of confidence intervals. Using similar mediation approaches, we will also examine whether cognitive differences between groups at 12 months are mediated by differences in PA adherence at 12 months.

Quantitative feasibility, acceptability, and intervention fidelity outcomes will be compared across sites and exercise type using analysis of variance or chi-square tests when applicable.

Qualitative analysis will be conducted for acceptability questions at 4 months and PA barriers and facilitators at 12 months. [name] and [name] have a history of designing and analyzing data from qualitative studies. Content analysis will be used to derive themes related to barriers and facilitators to long-term PA, which will be synthesized with quantitative data to examine correlates (e.g., demographics, health).

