## STUDY TIMELINE

We propose a 5-year timeline to accomplish our specific aims (**Table 1**). By conducting a rigorous, prospective, randomized clinical trial testing two exercise regimens, we will overcome limitations of previous studies investigating non-pharmacological approaches to improving the *healthspan* of people living with HIV. This design enables us to characterize the clinical (i.e., physical function and patient-reported fatigue) and translational (i.e., mitochondrial bioenergetics) effects of these interventions in an understudied, yet growing, population. To ensure that we meet enrollment and data collection milestones, we anticipate 4.5 full years of research procedures, with the remaining 6 months to finalize data analyses and disseminate the final study results.

R01 Cognitive substudy (HEALTH-COG) will leverage newly enrolled participants at the two sites of the parent HEALTH study (R01AG066562), add a University of Alabama at Birmingham (UAB) site, add new measures (psychological mechanisms of adherence, cognitive function, biomarkers) and a 12 month follow-up. This study is optional (to UCD/UW participants) and open to anyone enrolled in the parent HEALTH study. The sub-study R01 proposes to enroll/randomize 110 participants (UAB=60, University of Washington (UW)/University of Colorado Denver (UCD)=50 total between the two sites). Based on current enrollment numbers at the parent study sites (UCD=37 and UW=31), we anticipate it will be feasible for the new R01 to enroll the remaining participants across both sites (~32 participants), and due to timing of funding in relation to enrollment at UCD and UW, approximately 8-10 additional participants at both UCD and UW will need to enroll to meet and overall goal of 110 in this sub-study. The parent study end date is ~2 years into new R01 (yielding 2-3 additional years of study).

| Table 1.               |     |                      |   |
|------------------------|-----|----------------------|---|
| Timing
(Year/Month) |     | Enrollment
Target | Milestones  |
| Year 1                 | JIT |                      | 
 
Protocol & Manual of procedures finalized
 
IRB approvals
 
Hospital/research center approvals
 
Data transfer agreements between UCD-AMC and UW finalized and executed
 
  |

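### The EMA lag model uses a single unsplit mechanism score, so its slope blends between-person with within-person association and can show a lagged effect that no individual has

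*Combined protocol and SAP*

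**What the plan says.** The Cognitive Substudy Statistical Analysis gives one model for the EMA data. PA at interval T is regressed on MoA at T-1, time of day, day, site and covariates, with random effects for subject and for day within subject. Its stated purpose is to "examine the time-lagged effects of MoA variables occurring during a specified time interval (T-1) on PA". The lag may run from morning to later the same day or from one day to the next ("use the MoA in Day 1 to predict the PA in Day 2"). On adjustment, the plan says: "The covariates include significant distal predictors". The preceding paragraph lists those predictors as sociodemographics, physical health, randomised condition and changes in parent-trial outcomes. A person's own average MoA is not among them.

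The Cognitive Substudy section contrasts trait-level questionnaires with the text-message items, of which it says: "state-level) items reflect experiences in the moment". On the schedule it says "the EMA will include 7-days of twice daily texts", and on size, under Study Timeline, "The sub-study R01 proposes to enroll/randomize 110 participants".

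A later sentence plans a mediation analysis from intervention to MoA to PA by path analysis that respects the multilevel structure. No section mentions person-mean centring, a person-mean term, or separate between- and within-person effects.

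**The concern.** Two different statements could produce a positive slope. One is that people who are generally more confident or motivated are generally more active. The other is that the same person is more active after a moment of higher confidence. The lag sentence, and the state-versus-trait distinction, concern the second. A subject random intercept does not remove the first, because it assumes that the intercept is unrelated to MoA. The day-within-subject effect does not remove it either, and false discovery rate control deals with multiplicity, not with a blended coefficient.

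The risk is that stable differences between people are reported as momentary mechanisms of adherence. That would bear on claims about when prompting a person might help. The concurrent-effect models have the same gap.

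**Working it through.** The plan states no power, error rate or variance components for this model, so there is no figure to reproduce.

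**Inputs from the documents.** Seven days of two prompts give T = 6 day-to-day pairs, or at most 13 prompt-to-prompt pairs. N is 110. Applying the parent trial's 20% dropout to the substudy (an assumption) gives 110 × 0.8 = 88. Tests are two-sided. The 0.05 level is stated only for Aims 1 and 2 and is assumed here.

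**Assumed, not in the documents.** MoA intraclass correlation (ICC) ρ of 0.4 to 0.8; PA ICC of 0.2 to 0.5; a range of between-person associations; balanced data; no other covariates; a true within-person lag effect of zero.

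**1. What the slope estimates.** With MoA variance scaled to 1:

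- slope = w·b_between + (1 − w)·b_within
- w = ψS_B / (ψS_B + S_W)
- ψ = σ²_e / (σ²_e + Tσ²_u), the within- and between-person PA variances
- S_B = T[ρ + (1 − ρ)/T] and S_W = (T − 1)(1 − ρ)

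Middle case, T = 6, ρ = 0.6, PA ICC 0.5, between-person correlation 0.3:

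- ψ = 0.5/(0.5 + 6 × 0.5) = 0.143
- S_B = 6 × (0.6 + 0.4/6) = 4.0; S_W = 5 × 0.4 = 2.0
- w = 0.571/(0.571 + 2.0) = 0.22
- b_between = 0.3 × √(0.6 × 0.5)/(0.6 + 0.4/6) = 0.246
- expected slope = 0.22 × 0.246 = 0.055, although the within-person effect is zero

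Over MoA ICC 0.4 to 0.8 with 6 pairs, w is 0.17 to 0.67 for PA ICC 0.2 to 0.4, and 0.13 to 0.58 for PA ICC 0.3 to 0.5. With 13 pairs and PA ICC 0.3 to 0.5 it is 0.05 to 0.40.

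**2. False-positive rates by simulation** (REML random-intercept fits). In the middle case with N = 110, the model as written gave a mean slope of 0.053 and rejected 26.5% of the time; the split model rejected 5.8%. Over MoA ICC 0.4 to 0.8 and PA ICC 0.3 to 0.5, with 6 pairs:

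| Between-person correlation | N = 88 | N = 110 |
|---|---|---|
| 0 | not run | 4% to 6% |
| 0.3 | 11% to 44% | 17% to 54% |
| 0.5 | 32% to 91% | 39% to 95% |

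Across these and the 13-pair scenarios the split model rejected 2.8% to 7.3%, with a Monte Carlo standard error of about 0.9 points.

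Expressed as a between-person slope (6 pairs, MoA ICC 0.6, residual between-person PA variance 0.3), the model as written rejects about 5% to 7% at slope 0 and about 11% at 0.1. At slope 0.3 it rejects 43% to 47% with N = 88 and 51% to 56% with N = 110. The two scales agree: a slope of 0.3 explains 0.3² × 0.6 = 0.054 of the between-person PA variance, a correlation of √(0.054/0.354) = 0.39, between the lower two rows of the table.

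**3. Feedback from PA to MoA.** The near-5% rate of the split model needs PA not to alter later MoA. If a day's PA deviation shifts that day's MoA by 0.2 to 0.5 per unit (assumed), the split model rejects 16% to 61% of the time, with negative bias. The person mean over 6 pairs contains MoA values that carry the disturbance of the PA being predicted.

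**4. Mediation.** Arm is constant within a person, and deviations from a person's own mean average zero in every person, hence in every arm. The intervention cannot act through the centred term.

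**The case against.** The text never calls the score raw. The formulas in this section are shorthand without variable coding, and an analyst might centre by habit. That is fair, but the lag model is written out term by term and nothing in it requires a split.

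The size is wholly assumed, and the error rate is nominal when there is no between-person association. This stands. A reader might infer that roughly half of null mechanisms would be declared significant; the documents support no single rate. They do propose self-efficacy and motivation as mechanisms of maintained activity, so some between-person association is to be expected.

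A reader might also infer that only the within-person effect matters to the aim. The aim concerns long-term maintenance and habitual activity, so the between-person association is of interest too. The fault is in blending the two under the name of a lagged effect.

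A third tempting inference is that the blended lag coefficient passes into the mediation analysis and that the within-person term should replace it there. The plan describes a separate multilevel path analysis, focused on estimation, and does not say the lag coefficient is reused. Step 4 shows that the within-person term could not carry a randomised effect.

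The strongest objection is feedback. Evening items refer to exercise done that day, and some affect items are triggered by activity. With same-day feedback of 0.2, 0.3 and 0.5 and a between-person slope of 0.3, the model as written rejected 29%, 20% and 7% of the time, and at the two larger values it did better than the split model. Splitting is therefore necessary to answer the lagged question but not sufficient.

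**Conclusion.** The point holds with a condition. As written, the EMA slope is not a within-person lagged effect. It can be significant with no such effect if average MoA and average PA are associated beyond what the covariates capture. The mechanism follows from the model. The size rests on assumed variance components and ranges from no inflation to rejection in most samples when the between-person association is strong. The documents do not support saying that a spurious finding will occur, or that splitting alone guarantees a 5% error rate.

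The scope is limited: the substudy's secondary aim, listed for the trial as exploratory outcome 22. The primary 400-m walk analysis is untouched. Because the correction is cheap and the analysis bears directly on the substudy's question, it should be made before the EMA data are analysed.

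**What to change.** - **Lagged and concurrent EMA models:** replace the single MoA term with two, MoA minus the person's mean and the person's mean. Report the first as the lagged (or concurrent) within-person effect and the second as the between-person association.
- **Feedback:** pre-specify a sensitivity analysis. Adjusting for PA(T-1) is one option, but specify its coding: in a check with the same kind of simulation, PA(T-1) entered as a deviation from the person's mean brought the error rate back to about nominal under simple same-day feedback, whereas entering it uncentred made the bias worse. Neither version dealt with feedback to the next day's MoA. A joint model of MoA and PA with latent person means is the fuller alternative; Mplus is already among the named packages.
- **Mediation:** state that the two components are separated and that the person-level component carries the intervention-to-MoA-to-PA path. Do not use the within-person term there. The MoA-to-PA step remains an observational association.

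The cost is one extra model term, a sensitivity analysis and a somewhat wider interval for the lagged effect. No new data are needed.

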## G. Summarize Knowledge to be Gained:

This proposal addresses important questions with individual and public health relevance and is supported by a strong interdisciplinary team of investigators with a history of successful collaboration, and the resources to implement the proposed work. This proposal will provide precise, causal data on the clinical and translational effects of two promising exercise interventions that vary by intensity and interval in a representative sample of older PWH. These data have tremendous potential to impact care for the up to 50% of PWH with physical function impairments and prevalent and burdensome fatigue. If our hypotheses are confirmed, future work will include an implementation science study, harnessing networks such as the AIDS Clinical Trials Group, of which [name] is an active investigator, to roll-out larger scale trials in diverse settings where PWH receive care. Thus, the proposed study is likely to stimulate additional novel and significant research that will have far-reaching impact on the health and quality of life of older PWH.

## STUDY TIMELINE

We propose a 5-year timeline to accomplish our specific aims (**Table 1**). By conducting a rigorous, prospective, randomized clinical trial testing two exercise regimens, we will overcome limitations of previous studies investigating non-pharmacological approaches to improving the *healthspan* of people living with HIV. This design enables us to characterize the clinical (i.e., physical function and patient-reported fatigue) and translational (i.e., mitochondrial bioenergetics) effects of these interventions in an understudied, yet growing, population. To ensure that we meet enrollment and data collection milestones, we anticipate 4.5 full years of research procedures, with the remaining 6 months to finalize data analyses and disseminate the final study results.

R01 Cognitive substudy (HEALTH-COG) will leverage newly enrolled participants at the two sites of the parent HEALTH study (R01AG066562), add a University of Alabama at Birmingham (UAB) site, add new measures (psychological mechanisms of adherence, cognitive function, biomarkers) and a 12 month follow-up. This study is optional (to UCD/UW participants) and open to anyone enrolled in the parent HEALTH study. The sub-study R01 proposes to enroll/randomize 110 participants (UAB=60, University of Washington (UW)/University of Colorado Denver (UCD)=50 total between the two sites). Based on current enrollment numbers at the parent study sites (UCD=37 and UW=31), we anticipate it will be feasible for the new R01 to enroll the remaining participants across both sites (~32 participants), and due to timing of funding in relation to enrollment at UCD and UW, approximately 8-10 additional participants at both UCD and UW will need to enroll to meet and overall goal of 110 in this sub-study. The parent study end date is ~2 years into new R01 (yielding 2-3 additional years of study).

| Table 1.               |     |                      |   |
|------------------------|-----|----------------------|---|
| Timing
(Year/Month) |     | Enrollment
Target | Milestones  |
| Year 1                 | JIT |                      | 
 
Protocol & Manual of procedures finalized
 
IRB approvals
 
Hospital/research center approvals
 
Data transfer agreements between UCD-AMC and UW finalized and executed
 
  |
|                        | 3   |                      | 
 
Recruitment: Pre-screen potential participants, contact participants from database, advertisements/brochures in local clinics, provider meetings, presentations to community groups about study
 
Develop database and forms
 
Colorado site meeting with all investigators
 
Coordinate laboratory techniques between sites
 
 |
|                        | 6   | Begins               | 
 
Enrollment begins with goal of recruiting 2-3/month over 36 months
 
   |

|        |    |     |   |
|--------|----|-----|---|
|        |    |     | 
 
Monthly team meetings: review study progress, exercise session logs documenting progression, events (weekly PI/RA calls)
 
  |
|        | 9  | 9   | 
 
Prepare/submit Year 1 progress report & IRB continuing review
 
Revisit enrollment progress and recruiting strategies; readdress as needed
 
   |
|        | 12 | 18  | 
 
First participant completes the study
 
Prepare/meet with safety officer for q6 month review (after first patient enrolled)
 
Yearly site visit at Colorado
 
                    |
| Year 2 | 15 | 27  | Enrollment, study visits continue   |
|        | 18 | 36  | Q6 month DSMB meeting   |
|        | 21 | 45  | Prepare/submit Year 2 progress report & IRB continuing review   |
|        | 24 | 54  | 
 
Q6 month DSMB meeting
 
Yearly site visit at Colorado
 
Revisit enrollment progress and recruiting strategies, readdress as needed
 
  |
| Year 3 | 27 | 63  | Enrollment, study visits continue   |
|        | 30 | 72  | Q6 month DSMB meeting   |
|        | 33 | 81  | Prepare/submit Year 3 progress report & IRB continue review   |
|        | 36 | 90  | 
 
Q6 month DSMB meeting
 
Yearly site visit at Colorado
 
  |
| Year 4 | 39 | 95  | Enrollment, study visits continue   |
|        | 42 | 100 | 
 
Q6 month DSMB r meeting
 
Final participant enrolls
 
  |
|        | 45 | 105 | Prepare/submit Year 4 progress report & IRB continue review   |
|        | 48 | 110 | 
 
Q6 month DSMB r meeting
 
Ship samples to Colorado for mitochondrial activity/content
 
  |
| Year 5 | 51 | 115 | 
 
Last participant completes all study procedures
 
Data cleaned, code transcripts for Aim 3, data analyses for Aim 1, begin Aim 2; submit manuscript
 
Dissemination of results
 
 |
|        | 54 | 120 | 
 
Mitochondrial activity/content analyses completed
 
Data analyses, coding continues
 
  |
|        | 57 |     | 
 
Data analyses completed for Aim 2 and start Aim 3; dissemination results
 
Prepare/submit IRB continuing review to complete data analyses
 
  |
|        | 60 |     | Study completed, results disseminated to the research and participant community   |

| Table 1b. Participant Enrollment Goals for Each Year of the 28-week Intervention for R01 Cognitive Sub study UAB Site   |     |                |    |    |    |                |    |    |    |                |    |    |    |                |    |   |   |                |   |   |   |
|---|-----|----------------|----|----|----|----------------|----|----|----|----------------|----|----|----|----------------|----|---|---|----------------|---|---|---|
|   |     | YEAR 1         |    |    |    | YEAR 2         |    |    |    | YEAR 3         |    |    |    | YEAR 4         |    |   |   | YEAR 5         |   |   |   |
|   |     | 6/1/23—3/31/24 |    |    |    | 4/1/24—3/31/25 |    |    |    | 4/1/25—3/31/26 |    |    |    | 4/1/26—3/31/27 |    |   |   | 4/1/27—3/31/28 |   |   |   |
| Project Task  | Qtr | 1              | 2  | 3  | 4  | 1              | 2  | 3  | 4  | 1              | 2  | 3  | 4  | 1              | 2  | 3 | 4 | 1              | 2 | 3 | 4 |
| Target Enrollment (UAB)*  |     |                |    | 5  | 10 | 15             | 20 | 25 | 30 | 35             | 40 | 45 | 50 | 55             | 60 |   |   |                |   |   |   |
| Target UW/UCD participants for cognitive testing*†  |     | 10             | 20 | 30 | 40 | 50             |    |    |    |                |    |    |    |                |    |   |   |                |   |   |   |
| Note. *numbers are cumulative; †UCD/UW combined N=50 assumes leveraging ~30 participants and enrolling ~10 additional HEALTH participants at UCD and UW. Parent study end date is ~2 years into new R01. |     |                |    |    |    |                |    |    |    |                |    |    |    |                |    |   |   |                |   |   |   |

